CT24-WI-GL03-RF03 2.0 Non-Interventional Statistical Analysis Plan For Secondary Data Collection Study 01-Jun-2020 Page 11 of 17 related conditions of medical significance). The distribution of the PS will be reviewed and patients with a PS in the areas of nonoverlap and/or with extreme PS values might be excluded to improve validity (PS trimming). Each patient in the PS trimmed receifercept group will be matched on a ratio of 1:1 with patients in the PS trimmed concurrent external control using optimal nearest neighbour matching with a maximum caliper of 1%. Pre- and post-matching balance will be assessed using standardized differences between these two PS-matched groups. A negative control outcome may also be identified to evaluate the pre- and post-matching balance. There are different options that will be considered while modelling via PS. These include:

- 1. Calipers: range from [.01,.25]
- 2. Statistic (used to match treated to control subject): logit of PS, minimizing difference of PS, Mahalanobis distance
- 3. Ratio match (treatment-to-untreated): 1-to-1, 1-to-m

Exact matching can be included within the PS model. Exact matching will be done by gender. A binary variable will be created to specify race. The variable will have the value of "Yes" for "White" and "No" for all other values.

Standardized mean differences of the matched variables are the main criteria used to determine whether objective 1 is met. An external control dataset is confirmed (i.e., objective 1 is met) when all of the standard mean differences for the matched variables are less than 0.1.

After the concurrent external control is constructed by PS matching, descriptive statistics will be tabulated on patient demographic and baseline clinical characteristics between achondroplasia patients from PS-matched recifercept phase 2 trial cohort and those from PS-matched concurrent external control. Two-sample T-tests will be used for continuous variables, and chi-square tests for categorical variables assuming the distribution is normal. Frequency of primary, secondary and exploretary outcomes of interest and 95% confidence intervals will be computed.

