Another method to construct an external control for C4181005 for the purpose of estimating the Average Treatment Effect (ATE) of recifercept is Inverse Probability Weights (IPW). IPW will use PS to weight the observations prior to the analysis of height growth. Weights are calculated for each subject as 1/PS for Recifercept and 1/(1-PS) for the untreated group. Standardized differences between the untreated and Recifercept groups will be assessed both before and after weighting. Standardized mean differences of <10% may be considered a negligible difference.

7.2.2 Objective 2

Achondroplasia disease measures including height growth, anthropometric measurements, difference in functional status and health-related of life will be summarized using descriptive statistics.

Analyses of Height Z-Score and Arm-Span-to-Height Difference

If objective 1 is met, either a matched dataset – exclusively with a ratio of treated to untreated of 1:1 - via PS or a dataset augmented by IPW will be used to analyze height Z-Score. Baseline summaries of Height Z-score and Arm-Span to Height-difference and change from baseline a months 3, 6, 9, and 12 will be presented.

7.2.3 Safety Analyses

Not applicable.

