10.3 APPENDIX 3: DIAGNOSIS AND PROCEDURE CODES USED IN THE STUDY

Propensity Score Matching

proc psmatch data = adsl ;

class SEX DRUG WHITE ;

psmodel DRUG (treated = 'Recifercept') = SEX AAGE WHITE ;

match method = varratio (kmax = 4) distance = lps exact = (SEX WHITE);

assess lps allcov / weight = none plots = (barchart boxplot);

```
output out(obs = match) = outasa lps = _Lps matchid = _MatchID ;
```

run;

PFIZER CONFIDENTIAL

CT24-WI-GL03-RF03 2.0 Non-Interventional Statistical Analysis Plan For Secondary Data Collection Study 01-Jun-2020 Page 16 of 17

MMRM with Propensity Score Matching clusters

```
proc mixed data = ps_match_mmrm ;
    by paramcd ;
    class _MatchID usubjid sex drug (ref = 'Not Treated') ;
    model chg = month drug / s ; /*** s = Solution for Fixed Effects ***/
    random int month / subject = usubjid(_MatchId) ;
run ;
```

Inverse Probability Weighting

```
proc psmatch data = adsl region = allobs ;
    class SEX DRUG WHITE ;
    psmodel DRUG (treated = 'Recifercept') = SEX AAGE WHITE ;
    assess lps var = (SEX AAGE WHITE) / weight = atewgt plots = (barchart boxplot) ;
    output out(obs = all) = ipw_ate ATEWGT = _ATE_ ;
```

run;

MMRM with Inverse Probability Weights

```
PROC GLIMMIX DATA = ate_ipw METHOD = quadrature (qpoints = 27) EMPIRICAL =
classical NOREML ;
NLOPTIONS GCONV = 1E-10 TECHNIQUE = TRUREG ;
where PARAMCD APSBLFL = "Y" ;
CLASS DRUG (REF = "Not Treated") USUBJID ;
MODEL CHG = DRUG MONTH / SOLUTION ;
RANDOM INT MONTH / subject = USUBJID WEIGHT = _ATE_ ;
```

RUN;

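### The SAP text requires 1:1 matching, but its only matching code builds unweighted sets of up to four controls, so exact balance on sex and race can be lost and the 0.1 criterion judged on a different dataset

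*SAP*

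**What the plan says.** **Text.** SAP 7.2.2 says that the matched dataset used for Objective 2 is built "exclusively with a ratio of treated to untreated of 1:1". The main text of SAP 7.2.1 has each treated patient "matched on a ratio of 1:1 with patients in the PS trimmed concurrent external control", and protocol 9.6 uses the same words. SAP 7.2.1 then lists options to be considered while modelling, among them "Ratio match (treatment-to-untreated): 1-to-1, 1-to-m". It gives two caliper statements: a 1% maximum, and a range from .01 to .25.

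**Criterion.** Under SAP 7.2.1, Objective 1 is met "when all of the standard mean differences for the matched variables are less than 0.1". Objective 2 is analysed only if Objective 1 is met.

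**Code.** SAP 10.3 contains one MATCH statement: "match method = varratio (kmax = 4) distance = lps exact = (SEX WHITE". It names no caliper. Balance is assessed with "assess lps allcov / weight = none". The matched-set mixed model is "model chg = month drug / s", with "random int month / subject = usubjid(_MatchId". It has no WEIGHT statement. The match identifier appears only as the level within which subjects are nested.

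The code is not a leftover. Item 13 of the SAP's list of amendments says it was added in this version.

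**The concern.** Running the listed code gives a different dataset from the one SAP 7.2.2 prescribes. In variable-ratio sets, a treated child with four controls contributes four control records to the pool, and a child with one control contributes one. If set size varies with sex or race, the pooled controls no longer have the treated group's mix, even though every set was matched exactly on both. Nothing in the listed balance check or outcome model offsets this.

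Two things are at stake. The 0.1 criterion could be judged on a sample other than the 1:1 sample that SAP 7.2.2 says is analysed. If the variable-ratio sets are themselves analysed, an imbalance that the matching had removed re-enters the treatment contrast.

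**Working it through.** **1. No plan figure to reproduce.** The documents give no expected set sizes or SMDs. The only stated figure on balance is the 0.1 limit. Protocol Table 1 counts its sample sizes in pairs, which agrees with 1:1 matching and is not affected by this point.

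**2. Set-up.** Take a binary variable matched exactly, such as SEX or WHITE. Let *p* be the treated share in stratum A, and *r* the mean number of controls per treated child in A divided by that in B. The strata and values of *r* are illustrative.

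- Pooled, unweighted control share: *pc* = *p r* / (*p r* + 1 − *p*)
- SMD = (*pc* − *p*) / √{[*p*(1 − *p*) + *pc*(1 − *pc*)] / 2}

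**3. Results for *p* = 0.5.** For *r* = 2, *pc* = 1.0/1.5 = 0.667, and SMD = 0.1667/√[(0.25 + 0.2222)/2] = 0.1667/0.4859 = 0.343.

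| Controls per child, A vs B | *r* | *pc* | SMD |
|---|---|---|---|
| 2 vs 1 | 2.000 | 0.667 | 0.343 |
| 3 vs 2 | 1.500 | 0.600 | 0.202 |
| 4 vs 3 | 1.333 | 0.571 | 0.144 |
| ratio 1.2 | 1.200 | 0.545 | 0.091 |

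**4. Ratio that alone reaches 0.1.** For a 50/50 split, *r* = 1.222: *pc* = 0.550, and SMD = 0.05/0.4987 = 0.100. For a 70/30 split *r* is 1.25, and for an 80/20 split 1.30.

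**5. Under the stated rule.** With 1:1 matching, *r* = 1, so *pc* = *p* and the SMD is 0. With each control weighted by 1/(number of controls in its set), every set counts once on each side, and the SMD on SEX and WHITE is again 0.

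**6. Effect on the contrast.** Let the mean changes without treatment be μA and μB. With the same follow-up per child and no adjustment for the stratum, the treated mean would be *p*μA + (1 − *p*)μB and the pooled control mean *pc*μA + (1 − *pc*)μB. They differ by (*pc* − *p*)(μA − μB) in absolute size. At *r* = 1.2 this is 0.545 − 0.500 = 0.045, or about 4.5% of the between-stratum difference, in a sample that passes the criterion at 0.091.

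**7. Could all sets hold four controls?** Sets of equal size would remove the problem. That needs 63 × 4 = 252 controls. If the 63 trial patients are counted within the 300 and all 63 are included, 300 − 63 = 237 remain before eligibility is applied, fewer than 252. This is conditional. If the 300 are separate, 300 exceeds 252. If only 59 treated patients complete D183, 59 × 4 = 236, which is within 237.

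**The case against.** **The unweighted SMD is correct for the coded model.** The listed PROC MIXED is also unweighted, so the unweighted SMD describes the sample that it would analyse. This stands. A reader might infer that the balance statistic is miscalculated, but it is not: an SMD of 0.34 would be a true warning about that contrast. The fault is that the imbalance is avoidable, and that the sample is not the 1:1 dataset of SAP 7.2.2.

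**1-to-m is a listed option.** SAP 7.2.1 does allow it while the control is being built, so the code is not outside every part of that section. But SAP 7.2.2 then limits the analysed matched dataset to 1:1 without exception. If the criterion is judged on variable-ratio sets and the analysis uses 1:1, balance is certified on another dataset. If the coded sets are analysed, 7.2.2 is not followed.

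**The listing is partial.** PSMATCH writes outasa, while PROC MIXED reads ps_match_mmrm, and SAP 7.2.1 does not say which run or which weighting the 0.1 limit applies to. So the documents do not show that variable-ratio sets will be analysed. They show only that no reduction to 1:1 is documented.

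**The outcome model might adjust.** The text of SAP 7.2 lists age and gender as fixed effects. Had the code included gender, the shift through sex would be largely removed. The code has neither term, and race appears in neither version.

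**A failed run is not final.** This also stands. SAP 7.2.1 offers other matching options and inverse probability weighting, which uses no matched sets. The documents do not support saying that Objective 1 would be lost.

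**Conclusion.** The conflict between text and code is direct, stands in current text and should be corrected. Run as written, the code can discard exact balance on SEX and WHITE. With a 50/50 treated split, a set-size ratio of 1.22 between strata is enough to reach the 0.1 limit. A slightly smaller ratio of 1.2 passes and moves the pooled contrast by about 4.5% of the between-stratum difference in mean change. Under the stated 1:1 rule both effects on these variables are zero.

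The size rests on assumed set sizes, and the shift also on a pooled contrast unadjusted for the stratum. The documents give no set sizes, covariate distributions or between-stratum differences. The supported claim is therefore that the coded run can fail the criterion or pass with avoidable imbalance, not that it will. A reader might also infer that the planned numbers make unequal sets certain. They do so only if the 63 are counted within the 300 and all are included.

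**What to change.** **Preferred: make the code follow the text.**
- Change the MATCH statement in SAP 10.3 to optimal 1:1 with an explicit caliper.
- In SAP 7.2.1, state one caliper rule that reconciles the 1% maximum with the .01 to .25 range. Remove the 1-to-m option or mark it as exploratory.
- State that the 0.1 limit is judged on the same 1:1 dataset that is analysed. The unweighted balance check is then appropriate.

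The cost is one code statement and a few SAP sentences. The small downside is that some eligible controls go unused.

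**If 1-to-m is kept,** amend SAP 7.2.1, SAP 7.2.2 and protocol 9.6. Apply matched-set weights (1 for treated children, 1/number of controls in the set for controls) in both the balance assessment and the outcome model. This costs more: three text changes, a weight variable, and a specification for the weighted mixed model. For its inverse-probability-weighted analysis the SAP uses a separate GLIMMIX set-up rather than the listed PROC MIXED.

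Neither route settles the difference between the fixed effects in SAP 7.2 and those in the code, which needs its own reconciliation.

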7.2 STATISTICAL ANALYSES

To evaluate objective 2, mixed-effect, repeated measures (MMRM) models will be used. The fixed effects of treatment, visit, treatment-by-visit interaction, age and gender will be included. Visit will be modeled as a categorical covariate. (If the model does not converge then Visit will be modeled as a continuous covariate.) There will be random effects for both slopes (i.e. visit as a continuous variable) and intercept, clustered by subject nested within a propensity-score matched set or clustered by subject weighted by Inverse Probability Weights (see section 10.3). Random effects for slopes will be removed in the above models do not converge. Unstructured covariance matrix will be assumed for the model errors.

7.2.1 Objective 1

To construct a concurrent external control for Study C4181005, a propensity score (PS) will be created to achieve balance across covariates between achondroplasia patients from Study C4181005 and patients from Study C4181001 who meet all the eligibility criteria of Study C4181005. The PS will be estimated using standard logistic regression approaches with the "outcome" variable being the data source (whether patients were included in Study C4181005 and exposure to recifercept treatment) and the predictors being the variables associated with both the exposure (recifercept treatment) and the outcomes of interest (i.e. standing height & arm-span-to-height difference). This model will provide the predicted probability of being in the trial cohort relative to the concurrent external control cohort as a function of the covariates (the propensity score of being included in Study C4181005). The potential covariates may include demographics (e.g. age, gender, race and ethnicity), clinical characteristics (e.g. presence of achondraplasia-related complications, Tanner stage, and other non-achondroplasia-

PFIZER CONFIDENTIAL

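### SAP 7.2 and the programs in SAP 10.3 specify different models for the only stated hypothesis, and nothing says which governs; the coded treatment term falls short when an effect builds up over time and growth slopes vary between children

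*SAP*

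**What the plan says.** SAP 3.1 states one null hypothesis: mean change from baseline in height Z-score up to 12 months does not differ between treated and natural-history patients. It names no contrast. SAP 7.2 then describes the model:

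- Fixed effects: "The fixed effects of treatment, visit, treatment-by-visit interaction, age and gender will be included".
- Visit: "Visit will be modeled as a categorical covariate".
- Random effects: intercept and slope per subject.
- Residuals: "Unstructured covariance matrix will be assumed for the model errors".
- First fallback: "If the model does not converge then Visit will be modeled as a continuous covariate".
- Second fallback: "Random effects for slopes will be removed in the above models do not converge".

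SAP 10.3 gives the programs. The matched analysis has "model chg = month drug / s" and the IPW analysis has "MODEL CHG = DRUG MONTH / SOLUTION". MONTH is in neither CLASS list, so it enters as a straight line. Both programs have a random intercept and slope; neither has an interaction or a residual structure.

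The only pointer from 7.2 to the code sits in the clustering and weighting phrase ("clustered by subject weighted by Inverse Probability Weights (see section 10.3"). Item 13 of the SAP amendment list records that the code was added. Neither says whether text or code decides the fixed effects.

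**The concern.** Two analysts, one following 7.2 and the other 10.3, would report different treatment estimates from the same data, and both could claim to have followed the SAP. The amendment is dated to after last subject, last visit, so the choice would be made when the data already exist.

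The two models also answer different questions. In the 7.2 model the treatment difference can change from visit to visit. In the coded model DRUG is the only treatment parameter, a single constant shift. A growth treatment may well act gradually. If it does, part of the group difference looks like variation between children in slope, the random slope absorbs it, and DRUG is too small.

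**Working it through.** The documents give no effect size, variance or power for this model, so there is no stated figure to reproduce. Protocol Table 1 concerns a different null, a median ratio.

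**1. Text against code**

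| Feature | SAP 7.2 | 10.3 matched | 10.3 IPW |
|---|---|---|---|
| Visit | categorical | linear MONTH | linear MONTH |
| Treatment-by-visit | yes | no | no |
| Random intercept and slope | yes | yes | yes, carrying the weight |
| Residual structure | unstructured | none given | none given |
| Age, gender | yes | no | no |

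The first fallback makes visit continuous but keeps the interaction. The second removes the random slope, which the code keeps. No route in 7.2 ends at the coded model.

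**2. What DRUG estimates**

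Assumptions: visits at t = 3, 6, 9, 12 (SAP 7.2.2 lists these for summaries only), complete follow-up, known variances. Let s = t/12 = (0.25, 0.5, 0.75, 1), r = between-child SD of 12-month change / residual SD, a = intercept SD / residual SD, and f = true treatment difference by visit, with Month 12 = 1.

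V = a²11ᵀ + r²ssᵀ + I, and DRUG tends to (1ᵀV⁻¹f)/(1ᵀV⁻¹1). This is free of a, of arm sizes and of subject-level weights.

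With 1ᵀs = 2.5 and sᵀs = 1.875:

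- Linear effect, f = s: share of Month 12 = 2.5/(4 + 1.25r²). The visit average is 2.5/4 = 0.625, so the share of the visit average is 4/(4 + 1.25r²).
- Plateau at Month 6, f = (0.5, 1, 1, 1): share of Month 12 = (3.5 + 0.625r²)/(4 + 1.25r²). The visit average is 0.875.
- Complete by Month 3, f = 1: share = 1.

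| r | Linear, % of Month 12 | Linear, % of visit average | Plateau, % of Month 12 | Plateau, % of visit average |
|---|---|---|---|---|
| 0 | 62.5 | 100 | 87.5 | 100 |
| 0.5 | 58 | 93 | 85 | 97 |
| 1 | 48 | 76 | 79 | 90 |
| 2 | 28 | 44 | 67 | 76 |
| 3 | 16 | 26 | 60 | 68 |

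Example, linear, r = 2: 2.5/(4 + 5) = 0.278, and 0.278/0.625 = 0.444.

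Simulated REML fits of the matched model (linear effect, 30 and 60 pairs, 300 runs each) gave 57–58% of Month 12 at r = 0, 45–46% at r = 1 and 27–28% at r = 2. With a drug-by-month term added, the Month-12 contrast recovered 99–102%. So estimating the variances pulls DRUG down slightly, even at r = 0.

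Sensitivity, linear effect, r = 0.5/1/2/3, share of Month 12: 48/42/31/22% if half of each arm ended at Month 6 (an assumption with a = 1; eligibility needs only about six months), and 53/42/23/13% if the Month 1 visit listed for C4181005 in Protocol Table 3 entered the model for the treated arm only.

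**3. Power, linear effect**

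Set the effect so that the Month-12 contrast has 90% power, z = 1.960 + 1.282 = 3.242. Arm size then cancels. For DRUG, z = 3.242 × share × √[(a² + r² + 1)/(a² + (1 + 1.875r²)/(4 + 1.25r²))].

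Example, r = 2, a = 1: 3.242 × 0.278 × √(6/1.944) = 1.58, so power = Φ(1.58 − 1.96) = 35%.

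| | a = 0.5 | a = 1 | a = 2 |
|---|---|---|---|
| DRUG, r = 0.5 | 85% | 68% | 54% |
| Visit-average test, r = 0.5 | 89% | 75% | 60% |
| DRUG, r = 2 | 47% | 35% | 23% |
| Visit-average test, r = 2 | 90% | 84% | 71% |

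With a plateau at Month 6, DRUG has at least about 83%. With an effect complete by Month 3 it has about 95% or more, above the Month-12 test.

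**4. Type I error**

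Simulating the matched program under no effect (1,000 runs per setting) gave rejection rates of 5.7–6.5%. The IPW program, with maximum likelihood, empirical standard errors and weights, was not simulated.

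**5. Can the 7.2 model be fitted as written?**

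An unstructured covariance over four visits has 10 parameters. Intercept and slope variances make 12, but the rank is 10. The random effects are therefore not identified on top of the unstructured residual.

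**The case against.** The best defence is that SAP 3.1 sets no Month-12 target. If change up to 12 months means the average over visits, DRUG equals that average at r = 0 with known variances and recovers 93% of it at r = 0.5 for a linear effect; at r = 0.5 its power is 4 to 7 points below a visit-average test. An effect complete by Month 3 loses nothing. All of this stands, and it limits the size of the problem. It does not remove the conflict between text and code, nor the shortfall at larger r.

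SAP 7.2.4 and the headings in 10.3 call the analysis a repeated-measures mixed model, as 7.2 does, which suggests the code was simply not brought into line with the text. That is plausible, but it is not a rule of precedence. The WHERE line of the IPW program looks incomplete, so some text may have been lost there; a lost interaction would have to be missing from both programs, along with visit from both CLASS lists.

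This is a pilot, Objective 2 depends on Objective 1, and the protocol amendment says recifercept was discontinued. That lowers the practical stakes, but the comparison is still the only formal test in the SAP.

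A reader might infer that the coded analysis must understate the effect, or must lack power. The documents do not support this: they give neither variances nor a time course. A reader might also infer a false-positive problem. The simulation showed no material inflation for the matched program, and nothing was tested for IPW.

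**Conclusion.** The concern holds in this form. Text and code specify different models for the one stated hypothesis, no passage ranks them, and neither fallback bridges them. This needs no assumption about variances.

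The consequence is conditional. If the code is run and the effect builds up over time, DRUG is below the Month-12 difference, and below the visit average once r exceeds 0. For a linear effect it recovers from 62.5% down to 16% of Month 12, and from 100% down to 26% of the visit average, over r = 0 to 3. These figures rest on visits at months 3, 6, 9 and 12, complete follow-up and known variances. The power loss can be large or absent.

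Age and gender are a separate conflict inside the SAP: 7.2 includes them, while 5.4 lists no covariates and amendment item 6 removes them. The code agrees with 5.4.

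**What to change.** Make 7.2 and both programs state one mean model, and state each covariance explicitly.

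- **Both programs:** put VISIT in CLASS and add DRUG*VISIT to the MODEL statement.
- **Matched program:** replace the RANDOM statement with `REPEATED VISIT / SUBJECT=USUBJID(_MatchID) TYPE=UN`, and say in 7.2 that this analysis has no further random effects.
- **IPW program:** its weight sits in the RANDOM statement, so that statement cannot simply be deleted. State its covariance separately in 7.2: either keep the weighted random intercept and slope with empirical standard errors, or move the weight to a marginal weighted model with a robust variance.
- **Fallback:** on non-convergence use a simpler covariance, keeping categorical visit and the interaction.
- **Section 3.1:** name the contrast that tests the null (Month 12 or the visit average, the sponsor's choice) and list the visits that enter the model.
- **Separately:** reconcile age and gender between 7.2 and 5.4.

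The cost is SAP wording, code edits and one decision on the IPW covariance. No new data and no patient burden are involved.
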